## 1.2 SCHEMA

### 1.3 SCHEDULE OF ACTIVITIES (SOA)

Procedures	Pre-screening	Screening Week Day -8 to -2	Enrollment Day -1 to 0	Day 1 (+ 6 days)	Day 7 (+ 6 days)	Day 15 (+ 6 days)	Day 21 (+ 6 days)	Day 30 (+ 6 days)	Day 45 (+ 6 days)	Day 60 (+ 6 days)	Day 75 (+ 6 days)	Day 90 (+ 6 days)
Prospective patient identified (DEEP 6 or provider registry)	X											
Confirm eligibility and Informed Consent via telephone and REDCap	X											
Online Pain Intensity Journal (7 days)		X										X
Screening Week Online Baseline Survey (see below)		X										
Randomization			X									
Participant receives study intervention kit			X									
Technical onboarding call				X								
Intervention: Participant uses VR therapy program and wears Fitbit Charge 4 watch				X	-----							X
Online survey: NIH HEAL Minimum Dataset	X											X
Immersive Tendency Questionnaire (ITQ)  and Motion Sickness Propensity Survey 	X											
Treatment expectation question	X											
Simulator Sickness Questionnaire (SSQ)  and Presence Survey				X								
Online survey: Primary outcome: PROMIS® Pain Interference	X			X	X	X	X	X	X	X	X	X
Discontinuation of Treatment Questionnaire				X	X	X	X	X	X	X	X	X
PROMIS® Physical Function  , Anxiety  , Depression  , Sleep disturbance  ; Pain intensity/interference with Enjoyment of life/interference with General activity (PEG)  , PCS-6 	X				X		X	X		X	X	X
EMR data: Charlson Comorbidity Index  , CURES and EMR: Prescription Data	X											X
Perceived study arm question, treatments in the last 90 days question												X
Online survey: PHQ-2, GAD-2, PGIC, TAPS [1/2]	X											X
Remote technical support				X	-----							X
End of study procedure question												X

Procedures	Pre-screening	Screening Week Day -8 to -2	Enrollment Day -1 to 0	Day 1 (+ 6 days)	Day 7 (+ 6 days)	Day 15 (+ 6 days)	Day 21 (+ 6 days)	Day 30 (+ 6 days)	Day 45 (+ 6 days)	Day 60 (+ 6 days)	Day 75 (+ 6 days)	Day 90 (+ 6 days)
Event Assessment: AE, SAE and UP review and reporting				X	X	X	X	X	X	X	X	X

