To assess the efficacy of Skills-Based and Distraction VR via patients' global impression of change (PGIC). The objective will be considered achieved if there is statistical evidence of higher rates of self-reported improvement in either VR group compared to control (sham) VR.	The overall effect of treatment from study baseline to Day 90 as measured by the PGIC is an exploratory endpoint. This scale measures self-reported belief regarding efficacy of treatment. A favorable response of 5-7 on the PGIC indicates significant improvement occurred over the course of the study. We will test for a statistically significant difference in PGIC responses between either VR group and control (sham) VR.	This exploratory endpoint will act as a check on internal validity for Primary and Secondary endpoints, and a general assessment of satisfaction with treatment.  The PGIC has established validity in measuring self-reported global change in cLBP trials. 
To assess the efficacy of Skills-Based and Distraction VR in improving wearable measures of physical activity from baseline to Day 90. The objective will be considered achieved if there is statistical evidence of measured improvement in either VR group compared to control (sham) VR.	The change from study baseline to Day 90 in weekly total steps as measured by FitBit is an exploratory endpoint. Change in steps will also be examined for interaction effects on the primary outcome.	There is evidence that physical activity can improve mood, sleep, and general health, yet persons with chronic pain may limit their activity because of their pain.  Evidence suggests that activity monitors encourage increased function and correlate with improvements in mood among patients with chronic pain. 

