To assess the efficacy of Skills-Based and Distraction VR in improving wearable measures of sleep from baseline to Day 90. The objective will be considered achieved if there is statistical evidence of measured improvement in either VR group compared to control (sham) VR.	The change from study baseline to Day 90 in sleep quantity (total minutes asleep as well as "sleep efficiency", see Section 4.6.3 for more info) as measured by FitBit is an exploratory endpoint. Changes in the seconds in sleep will also be examined for interaction effects on the primary outcome.	There is evidence that physical activity can improve mood, sleep, and general health, yet persons with chronic pain may limit their activity because of their pain.  Previous versions of the skills-based program used in this study showed improvements in the sleep subscale of a pain interference measure. 
Exploratory Subanalysis		
To assess subgroup analyses for the change from baseline in PROMIS-PI. An MMRM	The impact of the following variables mentioned in section	See Section 9.4.7 for details.

OBJECTIVES	ENDPOINTS	JUSTIFICATION FOR ENDPOINTS
model will be used to test for treatment by subgroup interactions.	9.4.7 will be assessed to changes in the primary outcome.	

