#### 9.4.9 EXPLORATORY OUTCOMES

A few exploratory hypotheses have been considered:

Exploratory Outcome: Global impression of change with pain treatment using PGIC

Question: Which intervention is associated with patient's perceived change in condition due to treatment?

Dependent variable: patient's perceived change in condition as assessed by PGIC

Comparisons: Superiority for both of the following (1) Distraction VR therapy vs. sham VR therapy; (2) skills-based VR therapy vs. sham VR therapy, if there is a statistically significant difference in Skills based VR vs Sham VR then a third test will be completed (3) Skills-based VR therapy vs Distraction VR therapy

Exploratory Outcome: Quality of sleep over time by biometric data on Fitbit Charge 4 (total minutes asleep and sleep efficiency per night)

Hypothesis: Skills-based VR will lead to a greater improvement in sleep quality than distraction based VR or Sham VR.

Comparisons: Superiority for both of the following (1) Distraction VR therapy vs. sham VR therapy; (2) skills-based VR therapy vs. sham VR therapy, if there is a statistically significant difference in Skills based VR vs Sham VR then a third test will be completed (3) Skills-based VR therapy vs Distraction VR therapy

Exploratory Outcome: Depression over time as measured by PROMIS Depression (version 4)

Hypothesis: Skills-based VR will lead to a greater improvement in PROMIS Depression than distraction-based VR or Sham VR.

Comparisons: Superiority for both of the following (1) Distraction VR therapy vs. sham VR therapy; (2) skills-based VR therapy vs. sham VR therapy, if there is a statistically significant difference in Skills based VR vs Sham VR then a third test will be completed (3) Skills-based VR therapy vs Distraction VR therapy

Exploratory Outcome: Increased physical function over time as measured by total steps using biometric data

Hypothesis: Skills-based VR will lead to a greater improvement in physical activity than distraction-based VR or Sham VR.

Comparisons: Superiority for both of the following (1) Distraction VR therapy vs. sham VR therapy; (2) skills-based VR therapy vs. sham VR therapy, if there is a statistically significant difference in Skills based VR vs Sham VR then a third test will be completed (3) Skills-based VR therapy vs Distraction VR therapy

Exploratory Outcome: Improvement in physical function as measured by PROMIS physical function (version 6b)

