VR device metadata will be provided monthly by AppliedVR as CSV files containing timestamped records of content accessed at the individual device level. These records will feature a device-ID unique to each patient. A linking list containing study-IDs and device-IDs will be stored on a secure server behind the Cedars-Sinai firewall, and only associated with other study data following database lock. In order to monitor weekly adherence, study-staff will access a subset of the metadata limited to study-ID and timestamps of usage. These data will be subjected to QC procedures in a SAS/STATA environment.

Deidentified Fitbit data will be stored by a research-grade, IRB-approved service (Fitabase, San Diego, CA) as minute level data from Fitbit servers for all participants. This data will be retrieved as CSV files and linked to study data in a secure SAS/STATA environment before being subjected to QC procedures.

In order to maintain standard data definitions and structures, the data dictionary and proposed database structures reflect the Standard Clinical Data Interchange Standards Consortium's (CDISC) Study Data Tabulation Model (SDTM). The data elements and relationships described by this standard will facilitate information exchange with DAC. Furthermore, we will employ DAC's forthcoming approach to data cleanliness and completeness standards and notation.

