#### **4.4 Demographic and Baseline Characteristics**

We will summarize demographic and baseline characteristics both by treatment group and overall. Any time-to-event counts will be measured from the day of randomization. Body Mass Index (BMI) will be calculated according to:  $BMI = \text{weight (kg)} / (\text{height (m)})^2$ . Age will be calculated according to:  $Age = (\text{date of event} - \text{birth date} + 1) / 365.25$ . Weekly average opioid dosage will be calculated as a 7-day average of daily maximum milligrams morphine equivalent (MME) as prescribed. Mean activity measures will be calculated as weekly averages (e.g. weekly steps, weekly sleep minutes). Activity classification (i.e. sedentary versus light versus moderate, etc.) will be provided by FitBit and reported as such. Zip code will be matched to median income using census data as an aggregate measure of socio-economic status.

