#### *Biometric Data – Steps*

We will assess the change from study baseline to Day 90 by comparing the treatment groups, separately, to the control group using a MMRM analysis. The repeated measures are the change from baseline weekly steps obtained for all weeks between Baseline and Day 90. The model will include fixed categorical effects for treatment, week, and the baseline weekly steps as a continuous covariate. We will employ the Stata xtmixed command or the R lmer function from the lme4 package with restricted maximum likelihood estimation (REML) and an unstructured within-patient covariance structure for this model. We will evaluate the assumptions of this model, including normality, using residual and other diagnostic plots of model fit.

From this model, we will estimate least squares means, standard errors, treatment differences in least squares means, and 95% confidence intervals for each time point. Primary inference will be based on the treatment comparison of least squares means at Day 90 from this model, and a p-value will be presented for this time point only. The null hypothesis is that the mean difference in the primary endpoint between the experimental arms and the sham arm is zero, versus the alternative hypothesis that this difference is not zero.

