#### *Biometric Data – Sleep*

We will assess the change from study baseline to Day 90 by comparing the treatment groups, separately, to the control group using a MMRM analysis. The repeated measures are the change from baseline weekly minutes classified as “sleep” obtained at weekly intervals between baseline and Day 90. The model will include fixed categorical effects for treatment, week, and baseline weekly steps as a continuous covariate. We will employ the Stata xtmixed command or the R lmer function from the lme4 package with restricted maximum likelihood estimation (REML) and an unstructured within-patient covariance structure for this model. We will evaluate the

assumptions of this model, including normality, using residual and other diagnostic plots of model fit.

From this model, we will estimate least squares means, standard errors, treatment differences in least squares means, and 95% confidence intervals for each time point. Primary inference will be based on the treatment comparison of least squares means at Day 90 from this model, and a p-value will be presented for this time point only. The null hypothesis is that the mean difference in the primary endpoint between the experimental arms and the sham arm is zero, versus the alternative hypothesis that this difference is not zero.

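### The Fitbit endpoints are worded as weekly totals with no wear rule, so a part-worn week would lower steps or sleep minutes without any change in behaviour

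*Protocol*

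**What the plan says.** **Steps.** The protocol's endpoint (section 3, Tertiary/Exploratory) is a total: "The change from study baseline to Day 90 in weekly total steps as measured by FitBit is an exploratory endpoint". The SAP's model (Exploratory Endpoint Analyses, Biometric Data – Steps) uses every week: "The repeated measures are the change from baseline weekly steps obtained for all weeks between Baseline and Day 90".

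**Sleep.** Protocol section 3 has "The change from study baseline to Day 90 in sleep quantity (total minutes asleep as well as" sleep efficiency. Protocol section 9.4.9 words the same outcome as "total minutes asleep and sleep efficiency per night". The SAP model (Biometric Data – Sleep) says: "The repeated measures are the change from baseline weekly minutes classified as" sleep, at weekly intervals.

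**Derivation.** The one derivation rule is in SAP section 4.4 and is repeated in protocol section 9.4.5: "Mean activity measures will be calculated as weekly averages (e.g. weekly steps, weekly sleep minutes"). It gives no denominator.

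**Wear.** The protocol's schedule of activities (section 1.3) has "Participant uses VR therapy program and wears Fitbit Charge 4 watch" from Day 1 to Day 90. It sets no minimum hours, days or nights. Protocol section 10.1.9.1 says the Fitbit data are held "as minute level data from Fitbit servers for all participants".

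**The concern.** A weekly sum gains nothing from a day on which the watch is off. Unless the week is rescaled or excluded, the recorded value falls even though the participant is as active as before. The repeated-measures model can accommodate a week that is absent, under missing at random. It cannot recognise a week that is present but too low.

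At stake is what the steps and sleep-minutes endpoints mean. Follow-up is remote for 90 days, and the reminders in protocol section 6.4 are triggered by missing surveys, not by an unworn watch. A decline in wear could therefore be reported as a decline in activity or sleep. If wear also differed by arm, part of any treatment difference would be a difference in wear. Protocol section 3 also plans to examine changes in steps and sleep for interaction with the primary outcome, so the same error would enter that exploratory look.

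**Working it through.** The documents give no wear rate, standard deviation, effect size or power for the Fitbit endpoints, so there is no stated figure to reproduce. The check has two parts.

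**1. Does any provision deal with a part-worn week?**

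- SAP section 6.1 covers participants who discontinue early. It says nothing about days missing inside a week.
- SAP section 6.4 triggers imputation when the primary or key secondary endpoint is missing in more than 15% of patients. The Fitbit endpoints are neither. Its closing sentence extends similar thinking to missing responses in mixed models, but a part-worn week yields a value and so is not missing.
- Protocol section 10.1.9.1 sends Fitbit data through quality control without naming a wear check.
- The SAP sets rules for headset use (section 4.5, compliance and 70% module completion; section 4.2, use on 50% of days for the per-protocol set) but none for the watch.

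No provision covers it.

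**2. How large is the effect if the variable is a weekly total?**

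Let d be the daily value, taken as equal across days and unchanged by treatment, and w the days worn. Recorded total = d × w; true total = d × 7; proportional shortfall = 1 − w/7, whatever the value of d.

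- w = 6: 1/7 = 14.3%
- w = 5: 2/7 = 28.6%
- w = 4: 3/7 = 42.9%

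In steps, with an assumed 4,000 to 8,000 per day and two days off:

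- 4,000/day: 28,000 becomes 20,000
- 6,000/day: 42,000 becomes 30,000
- 8,000/day: 56,000 becomes 40,000

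In sleep, with an assumed 360 to 420 minutes per night, one unworn night removes 360 to 420 minutes from the week and two remove 720 to 840.

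Between arms, suppose mean wear differs by half a day to one day per week (assumed) and behaviour does not differ. The spurious difference is 0.5/7 = 7.1% to 1/7 = 14.3% of a full week. At 6,000 steps per day that is 3,000 to 6,000 steps per week. Across 4,000 to 8,000 per day, the half-day case gives 2,000 to 4,000. Equal wear gives no spurious difference under these assumptions.

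The steps and sleep models list treatment, week and a baseline covariate but no treatment-by-week interaction. The Day 90 contrast is therefore a treatment effect common to all weeks, so a wear difference in any week contributes to it.

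**Comparison with a mean per worn day.** For the 6,000-step participant with two days off, 30,000/5 = 6,000, the true value. This holds if worn days are representative of unworn ones.

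**The case against.** Several points on the other side stand.

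- A reader might infer that the plan counts unworn days as inactivity and unworn nights as sleeplessness. No passage says so. That is the default result of an unqualified sum, not a stated rule. The weekly-average wording in SAP section 4.4 and protocol section 9.4.5 could mean a mean over recorded days, which would remove most of the effect, and the per-night wording in protocol section 9.4.9 is close to what is wanted. But no denominator is given, the examples attached to the average are weekly quantities, and section 3 says total.
- A reader might also infer that sham participants will wear the watch less and that the treatment comparison is therefore biased. The documents give no evidence of this. Protocol section 4.1 expects the real headset to reduce control-arm attrition. A participant who stops both devices altogether mainly leaves weeks without data, which is a different problem from intermittent wear.
- Sleep efficiency is a ratio within recorded sleep and is not pulled down by unworn nights.
- The documents do not say which minute-level streams are held. From steps alone, a minute with no steps does not distinguish sitting still from a watch on the table.
- Baseline is defined as the screening week (protocol section 9.4.1), but the kit arrives at enrolment, so no pre-treatment Fitbit week is evident. The percentages above are therefore relative to a fully worn week, not to a documented baseline.
- The manual of operating procedures was not available and may contain a wear check. Neither document points to one, and the definition of an analysis variable belongs in the SAP.

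**Conclusion.** The point holds in limited form. The documents describe the same measures as a total, as an average with no denominator and (for sleep) per night, and they give no rule for non-wear. Computed as the weekly total that section 3 names, the value falls by 14.3% for each unworn day or night relative to a fully worn week, and the model treats it as fully observed. That arithmetic rests on days being equal; the step and minute figures rest on assumed daily values.

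It does not follow that the treatment comparison is biased. That needs wear to differ by arm, which is assumed here only to show scale. The endpoints are exploratory and tested outside the gatekeeping (SAP section 6.3), so the primary and secondary conclusions are unaffected. This is a minor-to-moderate improvement to exploratory endpoints.

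**What to change.** In SAP section 4.4, the SAP's Biometric Data subsections and protocol section 3, replace the weekly total with mean steps per worn day and mean sleep minutes per recorded night. Bring protocol sections 9.4.5 and 9.4.9 into line.

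- Define a worn day and a recorded night from the minute-level record, using whichever streams are held, and state which these are.
- Treat unworn days and nights as missing, not as zero.
- Set a week to missing below a minimum number of valid days, fixed before unblinding, with a sensitivity analysis at another cut-off. Four of seven is one example; the documents supply no threshold.
- Tabulate days and nights worn by arm and week, so that any difference in wear is visible.

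The cost is some programming on data already held and the loss of some weeks. A mean per worn day still assumes that worn days resemble unworn ones, which the wear table helps a reader to judge.

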## 4 STUDY DESIGN

### 4.1 OVERALL DESIGN

This research will be conducted as randomized, double-blind, sham-controlled, 3-arm Phase 2 study. Two immersive VR arms use a skills-based VR therapy program, EaseVRx, and a distraction-based VR therapy program, EaseVRx-Distraction, while the sham VR arm uses a VR headset to deliver two-dimensional (non-immersive) content. The primary hypothesis is that participants randomized to either skills-based VR therapy or distraction VR therapy will report meaningful improvements in PROs, improved biometric outcomes, and reduced opioid use compared to participants receiving a non-immersive sham VR control intervention. It is currently planned as a single-site study. However, the self-administered nature of the intervention and remote data collection would accommodate additional sites from the BACPAC consortium if deemed necessary in time.

Review of the VR clinical research literature indicates that the principal source of bias in this research has been lack of a control arm that effectively blinds the participant to the treatment allocation. This is the first study, to our knowledge, in which participants randomized to the control arm will use a VR headset that enables participants to experience the novelty of the hardware but limits their viewing to content that is neither immersive nor interactive. The experience of using EaseVRx-Sham is similar to watching a large-screen TV. Rather than viewing 360-degree, 3D, interactive content, participants in the sham arm can choose among 2D nature experiences accompanied by music selected to be neither relaxing nor distracting. EaseVRx-Sham has the same number and duration of experiences as EaseVRx, and the functionality of the user interface to access the experiences is the same. Modifications were made to the appearance of the user interface in order to remove aspects that were added for therapeutic benefit. Thus, the use of this specially designed sham program enables us to isolate the effect of VR immersion. We also expect that receiving a real VR headset will reduce attrition among participants randomized to the control arm.

### 4.2 SCIENTIFIC RATIONALE FOR STUDY DESIGN

The three-arm study design will allow us to determine whether a skills-based VR program that teaches exportable skills using CBT, guided meditation, and biofeedback-based breathing exercises outperforms conventional, distraction-based VR therapy in reducing cLBP. The 90-day study duration was chosen to assess whether VR therapy's efficacy extends beyond short-term analgesia and reduces the frequency and intensity of ongoing LBP through continuous use over a longer period. It also will enable us to evaluate longer-term change in other PROs and whether continued use of VR reduces opioid use. The

active control group (Sham VR) was designed to minimize bias related to the novelty of the hardware, addressing one of the deficits of prior studies.

#### 4.3 JUSTIFICATION FOR DOSE

Prior research has shown that daily use of VR for 10 to 15 minutes is effective in managing pain, plus use as needed for breakthrough flares of pain. The skills-based VR therapy program, EaseVRx, is a standardized 56-day program consisting of scheduled daily virtual experiences. Each VR treatment experience lasts between 2-16 minutes, with an average duration of 6 minutes. To minimize the risk of cybersickness, participants are instructed to complete one VR treatment experience at a time. Given the low-risk nature of VR, they also may repeat experiences such as relaxation, breathing exercises, and games at other times during the day, in response to their pain. After the 56-day program is completed, participants in this arm are instructed to continue daily use, choosing from among the treatment experiences. Participants in the distraction-based VR (EaseVRx-Distraction) and the sham VR also will be instructed to use the VR headset at least once daily, choosing from among the experiences available in their devices.

